17.1 Imaging Response Criteria (for schedule of evaluations see Section X)

The typical standard of care MRI protocol at each evaluation will be scored as follows:

17.1.1 Unresected Brain Metastases treated with radiosurgery

The response score will be rated as one of the following (follow-up MRI will be compared to the prior MRI scans):

Stable disease: Absence of disease progression of treated lesion.

Disease progression:

For lesions measuring **more than 5 mm** in the baseline (volumetric) scan: At least 50% increase in the product of the two largest perpendicular diameters (compared to the smallest product measured for the same lesion).

For lesions measuring **5 mm or less** in the baseline (volumetric) scan: At least 100% increase in the product of the two largest perpendicular diameters (compared to the smallest product measured for the same lesion).

Note: Radionecrosis will not be considered tumor progression.

17.1.2 Resected Brain Metastasis (i.e. surgical cavity)

Note: Tumor bed control is defined as the absence of new nodular contrast enhancement in the surgical bed. By definition a post-operative MRI brain scan is required as a baseline study. If there is *questionable* development of nodular enhancement in the surgical bed, this should be graded as stable disease recognizing follow-up studies will make this determination more certain (e.g. questionable area of nodular enhancement continues to grow and should therefore be coded as disease progression). If on a subsequent scan or on an additional imaging modality it is deemed as progression in the surgical cavity according to the criteria above, the date of progression diagnosis will be documented as the first time a new/progressing lesion was evident on a scan (i.e. backdated).

The response score will be rated as one of the following (follow-up MRI brain scans will be compared to the prior MRI brain scan):

Stable disease: Absence of new nodular contrast enhancement in the surgical bed.

Disease progression: Development of new nodular contrast enhancement in the surgical bed.

Note: Radionecrosis will not be considered tumor progression.

17.1.3 Distant Brain Status (excludes status of surgical cavity and any unresected lesions treated with SRS at time of trial enrollment)

The response score will be rated as one of the following (follow-up MRI brain scans will be compared to the prior MRI brain scan):

Stable disease: Absence of new lesions.

Disease progression: Any new lesion, seen on:

- a. Two consecutive axial slices, OR
- b. At least one slice in two separate planes.

A lesion is designated "Undetermined" as long as it does not comply with the definition of progression due to a new lesion. If on a subsequent scan or on an additional imaging modality it is deemed as cerebral progression according to the criteria above, the date of progression diagnosis will be documented as the first time a new/progressing lesion was evident on a scan (i.e. backdated).

17.1.4 Leptomeningeal Disease (LMD) Status.

1. The response score will be rated as one of the following (follow-up MRI brain scans will be compared to the prior MRI brain scan). It is recommended that if leptomeningeal disease progression is suspected, MRI imaging of the spine should be performed prior to CSF cytology:

Stable disease: Absence of new leptomeningeal lesions.

Leptomeningeal Disease (LMD) progression: Any new lesion:

a. New enhancement along the cranial nerves with neurologic symptoms

- b. New enhancement along the cerebellar folia or pial lining outside of thE surgical bed (treated PTV)
- c. Focal or diffuse leptomeningeal enhancement distant from treatment sites
- d. CSF cytology positive
- e. Leptomeningeal enhancement along the spine

A lesion is designated "Undetermined" as long as it does not comply with the definition of progression due to a new lesion. If on a subsequent scan or on an additional imaging modality it is deemed as leptomeningeal progression according to the criteria above, the date of progression diagnosis will be documented as the first time a new/progressing lesion was evident on a scan (i.e. backdated).

If there is leptomeningeal disease progression it will be classified as "local" vs. "diffuse" as defined below:

a) Local LMD: within 3 cm of the surgical bed respecting anatomic boundaries (e.g., tentorium, falx, etc.) with absence of evidence of diffuse LMD

b) Diffuse LMD: any LMD away from surgical bed and/or positive CSF

• Radionecrosis. Meeting any of the following criteria will qualify as radiation necrosis after prior SRS.

1. Pathologic diagnosis after either resection or biopsy revealing findings consistent with radiation necrosis with the absence of active tumor cells.

2. Conventional MR

a. Lesion quotient of < 0.3, where lesion quotient is defined as the proportional value of the maximum axial cross-sectional area of the T2-weighted defined lesion over the maximum axial cross-sectional area of the contrast-enhancing lesion on the T1-weighted post-gadolinium sequence on a comparable axial slice OR

b. Due to concerns of radiation necrosis, steroids initiated and follow-up scan (>1 month interval on repeat scan) reveals decrease in both edema and contrast of enhancing lesions that were concerning for radiation necrosis.

3. Centers that normally use PET, MR Perfusion, or MRS to determine a diagnosis of radionecrosis are permitted to use these modalities to diagnose radionecrosis as according to the local PI's best practice.

NOTE: Images for standard restaging time points should continue to use the same imaging modality as used at baseline.

References:

- 1. L. Nayak, E. Q. Lee, P. Y. Wen, Epidemiology of Brain Metastases. *Curr Oncol Rep.* **14**, 48–54 (2011).
- 2. E. A. Maher, J. Mietz, C. L. Arteaga, R. A. DePinho, S. Mohla, (2009), vol. 69, pp. 6015–6020.

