5.0 OBJECTIVES

We propose to conduct a highly controlled feeding study for 16 weeks to examine the effects of an individualized ketogenic or American Institute of Cancer Research (AICR) dietary approach on tumor response to targeted radiation therapy, as well the neural preservation in non-targeted areas of the brain. Our specific aims are as follows:

Primary objective: Assess the feasibility of maintaining a ketogenic versus AICR diet in patients with brain metastasis selected for radiosurgery. Endpoints:

- Circulating glucose (primary endpoint)
- Circulating ketones (primary endpoint)
- Retention
- Side-effects

Secondary objective: Assess the preliminary efficacy of the ketogenic versus AICR diet on tumor response to targeted radiation therapy. Endpoints:

• RECIST v. 1.1 will be utilized to evaluate responses to therapy

Exploratory objective: Assess the preliminary effects of the ketogenic versus AIRC diet on cognitive function and quality of life in BM individuals undergoing radiation therapy.

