6.0 STUDY DESIGN

This pilot study will be a single center, randomized controlled study of 24 participants with diagnosed BM (various primary disease sites) comparing the effect of a ketogenic (n=12) and AICR (n=12) diet. Randomization will be balanced by blocks of random sizes but no stratification due to the small sample size. Both groups will undergo a 16-week diet intervention. In an effort to maintain a patient centric focus and monitor changes in quality of life (QOL) all patients will complete psychosocial and behavioral inventories. These inventories aim to capture a holistic view on the proposed nutritional intervention during treatment. Primary outcomes will be determined at baseline, 8 weeks, and 16 weeks (see section 13 - Study Calendar) while patient-centric outcomes will be assessed every four weeks.

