16.7 Data Safety Monitoring Plan

The data and safety monitoring plan will involve the continuous evaluation of safety, data quality and data timeliness. Investigators will conduct continuous review of data and patient safety at their regular Disease Group meetings (at least monthly) and the discussion will be documented in the minutes. The Co-PIs of the trial will review toxicities and responses of the trial where applicable at these disease center meetings and determine if the risk/benefit ratio of the trial changes. Frequency and severity of adverse events will be reviewed by the Co-PIs and compared to what is known about the agent/device from other sources; including published literature, scientific meetings and discussions with the sponsors, to determine if the trial should be terminated before completion. Serious adverse events and responses will also be reviewed by the OSUCCC Data and Safety Monitoring Committee (DSMC). The Co-PIs will also submit a progress report biannually that will be reviewed by the committee per the DSMC plan. All reportable Serious Adverse Events (SAE) will also be reported to the IRB of record as per the policies of the IRB.

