17.0 STATISTICAL ANALYSES

Analysis Plan

Unless otherwise specified, all analyses will proceed on an intent-to-treat basis, and hypothesis tests will be two-sided and at the 5% significance level.

The primary objective is to assess the feasibility of maintaining a ketogenic versus AICR diet in patients with brain metastasis selected for radiosurgery. The primary measurements are blood levels of glucose and ketones. Measurements will be taken at baseline, 8 weeks, and 16 weeks. These biomarker outcomes will be analyzed using mixed effects linear regression with fixed effects for timepoint, diet group, their interaction, BMI, and sex. We will use subject-level intercept random effects to account for correlation between repeated measurements within subjects. The primary targets of inference are the treatment effects at each (post-baseline) timepoint. To test the two primary measurements at the two post-baseline timepoints, we will use a 4-way Bonferroni-Holm correction to account for multiplicity. Retention at week 8 and 16, as well as side effects, will be summarized and compared between diet groups.

To assess the preliminary efficacy of ketogenic versus AICR diet on tumor response to targeted radiation therapy, we will use a Chi-squared test for the association between treatment group and partial-or-complete response according to RECIST v1.1.

For the exploratory objective assessing the preliminary effects of the ketogenic versus AICR diet on quality of life in BM individuals undergoing radiation therapy, we will use the same linear mixed effects model as for the primary objective, but with the following quality-of-life endpoints as outcomes: Hearth Hope Index, SF-36, FACT-B, Brief Pain Inventory, and Brief Fatigue Inventory. Tests will be performed without multiplicity correction.

The mixed models used for the primary analyses are applicable to unbalanced data due to chance imbalances, missing data, or drop-out. We will assess the possible impact of non-random missingness using sensitivity analyses.

Power Analysis

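### The protocol does not provide for scoring MRI response, progression and radionecrosis without knowledge of diet arm, which leaves the tumour-response comparison open to avoidable assessment bias

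*Protocol*

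**What the plan says.** **Design.** Section 6.0 states: "This pilot study will be a single center, randomized controlled study of 24 participants with diagnosed BM". There are 12 patients per diet. On allocation it says only "Randomization will be balanced by blocks of random sizes but no stratification due to the small sample size", with nothing on masking of patients, staff or image readers.

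**Endpoint and test.** The secondary objective in section 5.0 is tumour response: "RECIST v. 1.1 will be utilized to evaluate responses to therapy". Section 13 repeats this. Section 17.0 plans the comparison: "we will use a Chi-squared test for the association between treatment group and partial-or-complete response according to RECIST v1.1". By its general rule, "hypothesis tests will be two-sided and at the 5% significance level".

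**Scoring.** Section 17.1 opens with "The typical standard of care MRI protocol at each evaluation will be scored as follows" and names no reader. Section 8.1 takes the images from standard-of-care MRI at baseline, 8 and 16 weeks. Doubtful enhancement in the surgical bed is held as stable until later scans decide. Lesions not yet meeting the new-lesion rule are held as undetermined, and a later progression call is backdated. Radionecrosis can rest on pathology, on a lesion quotient, on improvement after steroids started for suspected necrosis, or on advanced imaging for which centres are "permitted to use these modalities to diagnose radionecrosis as according to the local PI's best practice".

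**Review.** Section 16.7 says "The Co-PIs of the trial will review toxicities and responses of the trial" at disease group meetings.

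**The concern.** Three conditions for assessment bias occur together.

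- **The arm is known to those around the patient.** The two diets look different, research staff are in daily contact with participants, and ketone readings are reported daily to the coordinator and lead dietitian (dietary-intervention text after section 7.3.6; section 8.2).
- **A direction is expected.** Section 1 hypothesises a better response to surgery and radiation under ketosis. Section 3.1 expects less tumour growth, and the dietary-intervention text expects better outcomes at higher ketone levels.
- **Some calls need judgement**, and no section separates the person making them from knowledge of the arm.

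At stake is the only comparison of tumour response in the trial, which a larger study would draw on. Retention is also affected, and it is a listed endpoint of the primary objective: section 15 removes patients with documented progression, so a week-8 call can decide who is still there at week 16. An analysis plan cannot repair scores already assigned with knowledge of the arm, so this belongs in the protocol.

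**Working it through.** **1. The plan's own figure.** The protocol gives a design figure only for the primary biomarkers: 99% power with 12 completers per arm at a significance level of 0.0125. For a two-sample t-test the noncentrality is difference / (SD × √(2/12)).

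- Glucose: 2.3 / (1.077 × 0.408) = 5.23, giving power 99.05% on 22 degrees of freedom.
- Ketones: 0.34 / (0.16 × 0.408) = 5.20, giving power 98.99%.

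The figure reproduces. It says nothing about response, for which no figure is stated, and masked scoring would leave it unchanged.

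**2. Which outcomes the judgement calls reach.**

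| Call | Direct effect | Effect on the tested response |
|---|---|---|
| Radionecrosis rather than progression | Not counted as progression (17.1.1, 17.1.2); patient not removed on that ground (15) | Usually none: both sides are non-response |
| Doubtful enhancement held as stable | Delays a progression call (17.1.2) | Usually none, for the same reason |
| Undetermined lesion later called progression | Progression, backdated (17.1.3, 17.1.4); removal (15) | Indirect: may end a response or remove the patient |
| RECIST v1.1 response itself | Partial or complete response against the rest (17.0) | Direct |

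Section 17.1 scores stable disease or progression and has no partial or complete category. The tested endpoint therefore rests on sections 13 and 17.0, and the rule has to cover the RECIST score as well.

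**3. Sensitivity of the response comparison.** One patient in 12 is 1/12 = 8.3 percentage points of an arm's rate. Starting from equal true counts, the number of one-sided switches from non-responder to responder needed for p < 0.05 is:

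| Responders per arm | Uncorrected chi-squared | With Yates correction |
|---|---|---|
| 3 of 12 | 5 (p = 0.041) | 6 (p = 0.041) |
| 4 of 12 | 5 (p = 0.041) | 6 (p = 0.038) |
| 6 of 12 | 5 (p = 0.025) | 6 (p = 0.018) |
| 8 of 12 | 4 (p = 0.028) | not reached (all 12 gives p = 0.100) |

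**4. Illustration under assumptions.** The documents give neither a response rate nor a misreading rate. Assume no true diet effect, a true response rate p of 30% to 70% in both arms, and a share m of 10% to 30% of ketogenic-arm non-responders read as responders. The false difference is m × (1 − p), from 0.10 × 0.30 = 3 points to 0.30 × 0.70 = 21 points. By exact enumeration, the chance of p ≤ 0.05 is:

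| Test | No misreading | With misreading |
|---|---|---|
| Uncorrected | 4.9% to 6.4% | 5.1% to 20.4% |
| Yates | 1.7% to 2.3% | 1.8% to 10.3% |

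The estimate is easily moved. A false significant result needs substantial misreading in one direction.

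**The case against.** The strongest reply is that silence is not evidence of unmasked reading. The protocol names no reader, never calls the trial open-label, and refers to an imaging appendix that is not in the document at hand. A reader might infer from section 16.7 that the Co-PIs score the scans. The text says only that they review toxicities and responses when weighing risk and benefit. This stands: the supportable point is a missing safeguard, and no reader is shown to know the arm.

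Second, a reader might infer that a radionecrosis call changes response status. In most cases it moves a patient between two non-responder categories. This also stands; the direct effect is on progression and removal.

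Third, many criteria are numeric or fixed: 50% or 100% growth in the diameter product, a lesion quotient below 0.3, a slice rule for new lesions, and a default of stable for doubtful enhancement. These narrow discretion but do not remove it. The steroid route starts with a clinical decision, and the advanced-imaging route follows local practice.

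Fourth, this is a 24-patient feasibility pilot whose primary endpoints, glucose and ketones, are measured values. That limits the importance. It does not protect retention, or the week-16 values of patients removed for progression.

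**Conclusion.** The point holds in a limited form. The protocol does not provide for scoring scans without knowledge of the arm, in a setting where the arm is known to patients and diet staff and a benefit is expected. The response comparison is exposed to a bias that could be avoided cheaply, and judgement on uncertain or radionecrotic lesions bears directly on progression, removal and retention.

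The 8.3 points per patient is the step size with 12 per arm. The 3 to 21 point range depends wholly on the assumed rates. Neither estimates actual bias.

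Two further readings are not supported. Response is not the trial's only efficacy evidence, since section 5.0 also lists preliminary effects on cognition and quality of life. Nor do the documents show that cognitive testing is exposed to the same degree: section 9.0 uses standardised tests with fixed change thresholds, and its self-report measure could not be protected by masking an assessor.

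**What to change.** Add to sections 13 and 17.1 that whoever already scores the study MRIs assigns RECIST response, progression and radionecrosis for the research record from images labelled with the study code, without diet arm, ketone logs or diet notes. The score is locked before any unmasked discussion, including the disease group meetings of section 16.7. State also that diet staff do not score scans.

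Treating physicians keep full information for care. No visit, procedure, sample size or test changes, and no extra reader is called for. Study numbers on data forms (section 10) and subject codes (section 11) already exist, though for confidentiality.

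The cost is protocol wording and a small coding and scheduling burden. Section 3.2 says the group includes oncologists as well as diet experts, but no section states that a reader unaware of the arm is available, so the site should confirm this.
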